### 6.1 Analysis Sets

**Pre-Screened Set** – Subjects who have signed pre-screening consent.

**Screened Set** – Subjects who have signed main informed consent.

**Safety Analysis Set** – Screened subjects who have received at least one Investigational Medicinal Product (IMP) administration.

**Pharmacokinetic Set** – Subjects in the Safety Analysis Set, for whom the primary PK parameters can be calculated.

Subjects excluded from the analysis sets and the reason for their exclusion will be listed in Appendix 16.2 of the CSR.

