9. STATISTICAL METHODS

9.1 Statistical Analysis

Statistical analysis will be done by the sponsor or under the authority of the sponsor. Statistical analyses will be performed using Version 9.2 or higher of SAS® (SAS Institute, Cary, NC 27513). Details regarding the statistical methods and definitions will be provided in the Statistical Analysis Plan (SAP), and will include templates for the tables, figures and listings to be provided. The SAP will be finalized before the database lock; output for the IDMC will be finalized before the first subject receives the first dose of IMP. Any deviations from the SAP are to be justified in the clinical trial report. A general description of the statistical methods to be used to analyze the safety, PK, PD and preliminary efficacy data is outlined below.

In general, descriptive statistics and/or frequency tabulations will be presented overall and by dose (cohort), for single or multiple administration, and by mutated gene (sub-cohort). Listings and figures presenting individual data will be generated as appropriate.

Endpoints are described in Section 3.3.

An interim analysis will be performed when all subjects in cohorts 1 and 2 have completed 12 weeks of MAD treatment or discontinued earlier, or if the sponsor deems a risk/benefit analysis necessary at any time point.

The primary analysis will be performed when all subjects in all cohorts have completed 12 weeks of MAD treatment or discontinued earlier.

The final analysis will be performed when all subjects have completed 24 weeks of MAD treatment (12 weeks in the MAD part + 12 weeks in the MAD extension part; Week 25 visit) or discontinued earlier.

The interim, primary and final analyses will be performed on the Safety Analysis Set (see Section 9.3) for the primary objective. Secondary and exploratory objectives will be conducted on the Pharmacokinetic Set. Safety analyses (AE, clinical laboratory tests, physical examination, vital signs, and ECG) will be performed on the Safety Analysis Set. Results from the interim, primary, and final analysis will be described in the clinical trial report.

Note that after Week 24, all subjects will remain on treatment with weekly IMP administrations and bi-weekly (every 2 weeks) assessments until the last MAD3 subject has completed the MAD Week 25 visit. The data from this period for these subjects will be tabulated and listed in the clinical trial report but will not be taken into account in the statistical modeling.

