9.3 Selection of Subjects to be Included in the Analyses

Pre-Screened Set – Subjects who have a signed pre-screening consent.

Screened Set – Subjects who have signed main informed consent.

Safety Analysis Set – Screened subjects who have received at least 1 IMP administration.

Pharmacokinetic Set – Subjects in the Safety Analysis Set for whom the primary PK data are considered sufficient and interpretable.

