#### 3.3 Exploratory Endpoints

- Difference in mean change from baseline for clinical assessments in various affected clinical domains (respiratory, muscle strength and function, dysphagia) using the Pharmacokinetic Set by dose (cohort), for single or multiple administration, and by mutated gene (subcohort) at each post-baseline visit. The parameters to be analyzed for respiratory function are FVC (L), %FVC Predicted, FEV1 (L), %FEV1 Predicted, FEV1/FVC, MEP (cm H2O), %MEP Predicted, MIP (cm H2O), %MIP Predicted, Oxygen Saturation (%). The MyoGrip Test score will be used for analyzing muscle strength. The following parameters will be analyzed for muscle function; D1 Standing and transfers (%), D2 Axial and proximal motor function (%), D3 Distal motor function (%), Total MFM32 Score (%). Dysphagia will be assessed using the EAT-10 total score.
- Difference in mean change from baseline for PROMIS Questionnaire T-scores for the following domains (Anxiety, Depression, Fatigue, Pain Interference, Ability to Participate and Physical Function) using the Pharmacokinetic Set by dose (cohort), for single and multiple administration, and by mutated gene (subcohort) at each post-baseline visit.
- Comparison of proportion of CGI-I responders (responders defined as responding 1 or 2) using the Pharmacokinetic Set by dose (cohort), for single and multiple administration, and by mutated gene (subcohort) at each post-baseline visit.
- Comparison of proportion of PGI-C responders (responders defined as responding 1 or 2) using the Pharmacokinetic Set by dose (cohort), for single and multiple administration, and by mutated gene (subcohort) at each post-baseline visit.
- Comparison of proportion of Goal Attainment Scaling (GAS) Questionnaire responders (responders defined as responding ‘YES – MUCH BETTER’, ‘YES – A LITTLE BETTER’) using the Pharmacokinetic Set by dose (cohort), for single and multiple administration, and by mutated gene (subcohort) at each post-baseline visit.
- Comparison of means of ADA against DYN101 using the Pharmacokinetic Set by dose (cohort), for single and multiple administration, and by mutated gene (subcohort) at each post-baseline visit.
- Comparisons of the metabolic profile of DYN101 in blood and urine using the Pharmacokinetic Set by dose (cohort), for single and multiple administration, and by mutated gene (subcohort) at each post-baseline visit.

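### Functional, patient-reported, global-impression and biopsy endpoints are confined to the Pharmacokinetic Set, which rests on undefined primary PK parameters, so a dosed subject with valid clinical data could be dropped

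*SAP*

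**What the plan says.** Protocol 9.1 gives the general rule: "Secondary and exploratory objectives will be conducted on the Pharmacokinetic Set". Protocol 3.3.2, 3.3.3 and the synopsis repeat it endpoint by endpoint.

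SAP 3.3 follows. The clinical domains are summarised as "respiratory, muscle strength and function, dysphagia) using the Pharmacokinetic Set by dose (cohort" and the PROMIS scores as "Ability to Participate and Physical Function) using the Pharmacokinetic Set by dose (cohort". The first global-impression endpoint reads "Comparison of proportion of CGI-I responders (responders defined as responding 1 or 2) using the Pharmacokinetic Set", and PGI-C and GAS are worded the same way. SAP 3.2 puts muscle DNM2 mRNA and muscle DYN101 concentration on the same set. In SAP section 12, the 14.2 tables and figures and the 16.2.6 listings all carry the Pharmacokinetic Set in their titles.

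Membership is defined in two ways. SAP 6.1 takes Safety Analysis Set subjects "for whom the primary PK parameters can be calculated". Protocol 9.3 takes those "for whom the primary PK data are considered sufficient and interpretable". The Safety Analysis Set itself is "Screened subjects who have received at least one Investigational Medicinal Product (IMP) administration". The only other sets are Pre-Screened and Screened. There is no efficacy or PD set and no supporting analysis on all dosed subjects. SAP 6.1 does require exclusions and their reasons to be listed.

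SAP 8 and 10 cut the final reporting to the IDMC outputs plus FVC, MIP, Total MFM32 Score and PGI-C.

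**The concern.** Whether a plasma PK parameter can be computed says nothing about whether a spirometry value, an MFM32 score or a patient's global rating is valid. The rule still uses the first to decide whether the second is reported. The decision is taken after dosing, and its key term is undefined: SAP 6.2.12 lists nine parameters and ranks none of them.

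At stake is the loss of usable clinical data in an ultra-rare disease with about six subjects per dose level, and some selection in very small groups if the subjects who fail differ from the rest. The four efficacy endpoints kept for the abbreviated report all fall under the rule.

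**Working it through.** **No planned figure to reproduce.** Protocol 9.11 states that the sample size is not based on a power calculation. The check is therefore a reading of the set assignments, then of the sampling schedule, then simple arithmetic on group sizes.

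**Set assignments in SAP section 12.**
- Plasma concentrations and PK parameters: listings 16.2.5.3 and 16.2.5.4, Safety Analysis Set.
- PGI-C, respiratory function and MFM32: listings 16.2.6.3, 16.2.6.5 and 16.2.6.7, Pharmacokinetic Set.

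A subject who failed the PK criterion would therefore have PK data listed but clinical data left out. That sits badly with SAP 6.3, 6.13.3, 6.13.5 and 6.13.6, which say that all data will be listed.

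**Who could fail (protocol Table 3).**
- SAD: 6 samples on Day 1 plus 8 later = 14, the last at 16 weeks.
- MAD Week 1: 6 + 3 = 9, the last at 167 h. MAD Week 12: 9. Week 25: 1.
- Total 14 + 9 + 9 + 1 = 33, which agrees with protocol Table 4.

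Protocol 1.3.1 gives a terminal half-life of 21 days in monkeys, and protocol 1.5 a distribution phase of about 24 to 48 h. If the human half-life were similar (an assumption):
- SAD follow-up covers 112/21 = 5.3 half-lives, with samples at 167 h and at 2, 4, 8, 12 and 16 weeks after the distribution phase.
- The MAD Week 1 profile covers (167/24)/21 = 0.33 of a half-life, with only the 71 h and 167 h samples after the distribution phase. A log-linear slope through two points leaves no residual degrees of freedom.

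A subject who went through SAD should be evaluable on almost any choice of primary parameter. A replacement who starts in MAD (protocol 3.1.2) has enough samples for Cmax, AUClast and AUCτ, but λz and AUC∞ could be judged not calculable. The answer depends on the undefined term.

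**Size of one exclusion.** The inputs are about 6 subjects per dose level and up to 3 with an MTM1 mutation (SAP 4).

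| Group | Share lost, 1/n | SE factor, √(n/(n−1)) | Mean shift if the excluded subject differs from the rest by 1 SD, 1/n |
|---|---|---|---|
| All, n = 18 | 5.6% | 1.03 | 0.06 SD |
| Dose level, n = 6 | 16.7% | 1.10 | 0.17 SD |
| MTM1 sub-cohort, n = 3 | 33.3% | 1.22 | 0.33 SD |

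For PGI-C, one responder among six (16.7%) becomes 1/5 (20%) if a non-responder is dropped, or 0/5 if the responder is dropped.

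**How often.** The documents give no non-evaluable rate. Purely as illustration, with a common rate p for all 18 subjects, the chance of at least one exclusion is 1 − (1 − p)^18. This is 0.305, 0.603, 0.850 and 0.982 for p = 2%, 5%, 10% and 20%. The SAD sampling suggests that a common rate overstates the risk for most subjects.

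**The case against.** The strongest reply is that the rule may exclude nobody. Membership is defined per subject, not per trial part. All subjects pass through SAD unless they enter as replacements, and SAD sampling is dense and long. If Cmax is primary, failures would be rare. This stands: a reader might infer that dosed subjects are in fact being excluded, and no passage shows that.

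A second reply is that the stakes are low. No hypothesis is tested (protocol 2.4), the models are not meant for inference (protocol 9.10), and the primary endpoint uses the Safety Analysis Set, as do vital signs, laboratory data and ECG in SAP 3.2. This also stands. It rules out any claim about error rates, and nothing in the documents links PK evaluability to FVC, MFM32 or PGI-C, so bias is a possibility and not a finding.

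A third reply concerns scope. Antibody results are used mainly to explore their effect on PK (protocol 9.9, SAP 6.12.2), and their planned listing was on the Safety Analysis Set before it was struck out. Muscle DYN101 concentration is itself an exposure measure. For these two, a PK-based set is defensible, and a claim that every endpoint on the set is misplaced would go too far. The muscle-biopsy listing is also struck out, so the reporting effect there may be nil.

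A fourth reply is that exclusions and reasons will be listed and that SAP 6 allows extra tables. That helps only in part, because the listed reason does not bring back the clinical values.

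**Conclusion.** The point holds as a flaw in the rule, with a conditional consequence. Both documents tie endpoints that need no plasma PK to a set whose entry test is undefined and worded differently in each, and no analysis on all dosed subjects offsets this.

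If one subject failed, a dose level would lose 17% of its data, or a full MTM1 sub-cohort 33%, in the FVC, MIP, Total MFM32 and PGI-C summaries and listings. These figures assume the target group sizes are reached. The route through a MAD-only replacement further assumes that λz or AUC∞ is primary and that the human half-life is of the order seen in monkeys. If no subject fails, the two sets coincide and no number changes. The documents do not support saying that the efficacy results are biased or that the safety conclusions are affected.

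**What to change.** - Summarise and list the exploratory efficacy, patient-reported and global-impression endpoints on the Safety Analysis Set, using all dosed subjects with the assessment. At minimum do this for FVC, MIP, Total MFM32 and PGI-C. Treat DNM2 mRNA the same way where it is reported.
- Keep the Pharmacokinetic Set for plasma PK summaries and PK-linked antibody analyses.
- State in SAP 6.1 which PK parameters are primary, and resolve the difference from the test in protocol 9.3.
- Align SAP 3.2, 3.3, 6.1 and the section 12 titles, including the 16.2.6 listings.
- Record the departure from protocol 9.1, 9.3, 3.3.2, 3.3.3 and the synopsis in SAP section 10, or amend those passages. Changing protocol 9.1 alone would create new contradictions.

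The cost is document wording and one population flag in the programs. No new data are needed.

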## **6.2 Derived Data**

This section describes the derivations required for statistical analysis. Unless otherwise stated, variables derived in the source data will not be re-calculated.

### **6.2.1 Age**

Year of birth and age at the time of informed consent is collected in the CRF.

### **6.2.2 Race**

Where more than one race category has been selected for a subject, these race categories will be combined into a single category labeled “Multiple Race” in the summary tables. The listings will reflect the original selected categories.

### **6.2.3 Baseline**

Baseline is defined as the last non-missing value (either scheduled, unscheduled or repeat) before the subject receives the first dose of study drug. The same baseline will be used for all SAD, MAD and MAD extension parts using the last available records before first dose of study drug in SAD part.

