1.1.2 Autosomal Dominant CNM

The clinical phenotypes of ADCNM range from mild and moderate forms in adult patients to severe forms in infants. In general, adolescent and young adult patients with moderate phenotype have moderate skeletal muscle weakness associated with ptosis and ophthalmoplegia and had delayed motor milestones as children. Pediatric patients usually have generalized weakness, hypotonia, moderate degree of facial weakness with open mouth, ptosis, and ophthalmoplegia (Romero and Bitoun, 2011). Many children with the disease also have stiff joints and sideways curvature of the spine (scoliosis). In childhood, as in the neonatal period, there is a risk of respiratory failure which can become life-threatening in serious situations (e.g. if the patient develops pneumonia). Adults may experience respiratory failure, which in turn may cause cardiac insufficiency. A significant portion of patients become wheelchair-dependent in their fifties (Bitoun et al., 2005; Verhaart et al., 2017a; Verhaart et al., 2017b; [name], 2017).

ADCNM is caused by mutations in the *DNM2* gene on chromosome 19p13.2 (Bitoun et al., 2005). Dynamins are structurally complex proteins composed of 5 different domains. CNM-causing mutations identified to date mainly localize to the middle domain involved in protein self-assembly and centrosome localization.

The incidence of ADCNM is currently unknown, although it has been reported to account for approximately 50% of CNM cases (Romero, 2010). The patient pool is estimated to have 553 prevalent cases worldwide (Vandersmissen et al., 2018). No NHS data of ADCNM have been published to date.

The prognosis of ADCNM is currently unknown. However, it appears to be quite heterogeneous, with some patients exhibiting a rapid deterioration and others a slow progressive loss of muscle function.

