3.1.1 Overview of Trial Periods

This is a first-in-human, Phase 1/2, open-label, multi-center trial to evaluate the safety, tolerability, PK, PD and preliminary efficacy of DYN101 after SAD and MAD in subjects ≥ 16 years of age* with CNMs caused by mutations in *DNM2* or *MTM1* (*for Germany, the subject must be ≥ 18 years of age in accordance with local and national regulations).

Sufficient subjects will be screened in order to ascertain that approximately 18 subjects will be dosed and finish the trial. Subjects may be recruited from an ongoing NHS (Nat-His-CNM Trial Protocol, 2017).

There will be stand-by subjects for replacement of subjects who discontinue the trial early, if needed. Stand-by subjects will perform run-in visits until the last MAD subject has completed Week 13, unless needed for replacement.

The trial will consist of a pre-screening consent, a screening period, a run-in period (if applicable), a SAD part with 4 weeks of follow-up after IMP administration and a washout period of at least 12 weeks (followed by follow-up phone calls until the MAD part starts), a MAD part of 12 weeks, and a MAD extension part of 12 weeks. All subjects will participate in the SAD, MAD and MAD extension parts, unless they withdraw. End of Treatment (EoT) assessments will be performed after 24 weeks of MAD treatment have been completed, i.e. at the Week 25 visit. Subjects will return to the clinic 3 months after the last IMP administration, to follow-up on the subject's status including abnormal laboratory results, AEs, and concomitant medications. The trial design is presented in Figure 1.

Abbreviations: BL: baseline, EoT: End of Treatment, FU: follow-up, MAD: multiple ascending dose, SAD: single ascending dose, SCR: screening, W: week

* All subjects will remain on treatment with weekly IMP administrations and bi-weekly (every 2 weeks) assessments until the last MAD3 subject has completed the MAD Week 25 visit. The data generated from these bi-weekly assessments will not be part of the statistical analysis for this trial (see Section 9.1).

Figure 1: Trial Design: Trial Periods

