Subjects will give a 'pre-screening' consent to be entered as 'pre-screened' in the Interactive Response Technology (IRT) system. The pre-screening consent process can be managed remotely (please refer to the Site Operations Manual for more details). Subsequently, subjects will sign the main informed consent form (ICF) and screening will be performed to assess eligibility. Subjects who are participating in the NHS and have at least 2 data time points available from the NHS to assess their pre-trial condition do not require a mandatory run-in visit.

Subject screening should be performed within 6 weeks before the baseline visit. There should be a minimum of 3 data time points to assess their pre-trial condition. The screening visit can be the third data time point.

Subjects who have not participated in the NHS or who do not have at least 2 data time points from the NHS will have a mandatory run-in period before continuing to the baseline visit. At least 1 run-in visit needs to be performed for these subjects in order to obtain 3 data time points to assess their pre-trial condition; screening can be the first data time point, baseline can be the third data time point. There should be a minimum of 28 days between screening and the first run-in visit. Run-in visits may be repeated until the assigned cohort can start (see Section 6.1.2). The run-in period is optional for stand-by subjects who participated in the NHS and have at least 3 data time points.

At baseline, subjects will be enrolled into the trial (if all in- and exclusion criteria are still met) until recruitment in the last cohort is reached, including replacement subject(s) who were amongst the stand-by subjects. Stand-by subjects will perform run-in visits until the last MAD subject has completed Week 13, unless needed for replacement.

In the SAD part, subjects will receive a single dose of IMP at Day 1. In the MAD part, subjects may receive the same or a different dose as in the SAD part, with weekly administrations of IMP for a period of 12 weeks, followed by a MAD extension part with an additional 12 weeks of treatment (weekly administrations). After Week 24, all subjects will remain on treatment with weekly IMP administrations and bi-weekly (every 2 weeks) assessments until the last MAD3 subject has completed the MAD Week 25 visit. In order to avoid any overlaps, a given MAD cohort may not start before its corresponding SAD cohort is finished.

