6.1.3.3 Multiple Ascending Dose Part

For subjects for whom the last visit in the SAD part was more than 3 months before the baseline visit in the MAD part, there will be an unscheduled visit (physical examination and clinical laboratory parameters) which will occur between 6 weeks and 7 days prior to the MAD baseline visit. Liver ultrasound and hepatic elastography have to be performed before the baseline visit in the MAD part. The first IMP administration in the MAD part cannot be started before the liver ultrasound and hepatic elastography results are available.

Subjects will receive weekly IV administrations of DYN101 for a period of 12 weeks, i.e. from MAD Week 1 to Week 12.

Replacement of withdrawn subjects can occur under the circumstances described in Section 3.1.2. New subjects who did not participate in the SAD part should sign an ICF for participation in the MAD part, and the eligibility will be assessed (see Section 6.1.1) before the first IMP administration in the MAD part (MAD Week 1 Day 1). Replacement subjects may or may not need a run-in period, in consultation with the sponsor (see Section 6.1.2). A DNA sample (optional) and a muscle biopsy should be taken before the first IMP administration.

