6.2.3.1 Collection of Blood Samples for PK Evaluations

Blood samples for the determination of DYN101 levels in plasma will be collected by an indwelling catheter in the arm into vacuum tubes at the time points indicated in [Table 3](#). A sample should be taken immediately after the end of the infusion. The following post-dose samples should be taken relative to the end of the infusion.

Table 3: Pharmacokinetic Sampling Schedule

Time Point	Time Relative to Dosing on Day 1 (SAD/MAD)	Sampling Window
SAD and Washout		
Week 1, Day 1	Pre-dose (0h)	
	30 min after start of infusion (i.e. during infusion)	±10 min
	Immediately after the end of infusion	±10 min
	1h after the end of infusion	±10 min
	3h after the end of infusion	±10 min
	7h after the end of infusion	±1h
Week 1, Day 2	23h after the end of infusion	±3h
Week 1, Day 3	47h after the end of infusion	±3h
Week 2, Day 8	167h after the end of infusion	±1d
Week 3, Day 15	2 weeks post-dose	±3d
Week 5, Day 29	4 weeks post-dose	±3d
Week 9	8 weeks post-dose	±3d
Week 13	12 weeks post-dose	±3d
Week 17	16 weeks post-dose	±3d

Time Point	Time Relative to Dosing on Day 1 (SAD/MAD)	Sampling Window
MAD		
MAD Week 1, Day 1	Pre-dose (0h)	
	30 min post start of infusion (i.e. during infusion)	±10 min
	Immediately after the end of infusion	±10 min
	1h after the end of infusion	±10 min
	3h after the end of infusion	±10 min
	7h after the end of infusion	±1h
MAD Week 1, Day 2	23h after the end of infusion	±3h
MAD Week 1, Day 4	71h after the end of infusion	±3h
MAD Week 2	Week 1, Day 1* 167h after the end of infusion	±1d
MAD Week 12, Day 1	Pre-dose (0h)	
	30 min after start of infusion (i.e. during infusion)	±10 min
	Immediately after the end of infusion	±10 min
	1h after the end of infusion	±10 min
	3h after the end of infusion	±10 min
	7h after the end of infusion	±1h
MAD Week 12, Day 2	23h after the end of infusion	±3h
MAD Week 12, Day 4	71h after the end of infusion	±3h
MAD Week 13	Week 12, Day 1* (167h after the end of infusion)	±1d
MAD Week 25	Week 24* (167h after the end of infusion)	±1d

* Sample to be taken before the next infusion (if applicable).

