9.8 Safety Analyses

Safety analyses will be presented for the Safety Analysis Set.

Baseline for all clinical laboratory tests, physical examination results, vital signs, liver ultrasound and hepatic elastography, and ECG will be defined as the last assessment prior to IMP administration.

Safety data will be analyzed using descriptive statistics (arithmetic mean, geometric mean, SD, %CV, median, minimum and maximum values, including 95% confidence intervals (CIs), if applicable).

Adverse Events

AEs will be coded using the MedDRA version available at the start of the trial. The number of events as well as the incidence and percentage of subjects with treatment-emergent adverse events (TEAEs) will be calculated overall, by system organ class, and by preferred term. TEAEs will be further summarized by severity and relationship to IMP. AEs related to IMP, AEs of special interest, AEs leading to withdrawal, SAEs and deaths will be summarized or listed.

Clinical Laboratory Tests

Descriptive statistics of observed values and changes from baseline will be calculated for each laboratory analyte at each scheduled time point. The frequency counts and percentage of subjects with laboratory abnormalities will be tabulated at each scheduled time point. The laboratory abnormalities will be determined according to the CTCAE criteria (version 5, November 2017) and in accordance with the normal ranges of the clinical laboratory if no gradings are available. Potentially clinically important findings will also be summarized or listed.

Physical Examination

Physical examination abnormalities will be listed at each scheduled time point.

Vital Signs and ECG

Descriptive statistics of observed values and changes from baseline will be calculated for each vital signs and ECG parameter at each scheduled time point. The frequency counts and percentage of subjects with abnormalities for each parameter will be tabulated at each scheduled time point.

Liver Ultrasound and Hepatic Elastography

The observed data for liver ultrasound and hepatic elastography assessments will be listed.

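### SAP 6.2.3 gives MAD visits only a pre-SAD baseline, so MAD change and shift tables for SAD participants reach back at least 16 weeks before the first MAD dose

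*SAP*

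**What the plan says.** SAP 6.2.3 first defines baseline as the last non-missing value before a subject's first dose. It then adds: "The same baseline will be used for all SAD, MAD and MAD extension parts using the last available records before first dose of study drug", and the sentence ends by naming the SAD part. No second baseline or sensitivity summary is planned. Protocol 9.8 says only that baseline for the safety measures "will be defined as the last assessment prior to IMP administration", without saying which administration.

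Protocol 3.1.1 describes "a SAD part with 4 weeks of follow-up after IMP administration and a washout period of at least 12 weeks", after which phone calls continue until the MAD part opens. It also says: "In the MAD part, subjects may receive the same or a different dose as in the SAD part".

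The protocol recognises a separate MAD baseline visit. Section 6.1.3.3 adds an unscheduled visit in one case: "For subjects for whom the last visit in the SAD part was more than 3 months before the baseline visit in the MAD part". Pre-dose laboratory tests, coagulation, complement, vital signs, ECG, respiratory function and MFM32 are scheduled for MAD Week 1 Day 1.

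The secondary endpoint in SAP 3.2 compares mean change from baseline in vital signs, laboratory data and ECG for single and for multiple administration. SAP 6.13.5, 6.14.2 to 6.14.4 and 6.14.6 plan shift tables from baseline to the worst result within each trial period.

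**The concern.** There is no control arm. After early termination, SAP 10 limits reporting to the IDMC outputs plus FVC, MIP, Total MFM32 and PGI-C, so for the first three the simple change tables carry much of the result. A MAD change that starts before the single dose combines three things: any response to that dose, the untreated wait, and multiple dosing. Only the last is what the endpoint calls multiple administration.

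The wait need not be neutral for every subject. Protocol 1.1.2 says the prognosis of the autosomal dominant form is unknown but appears heterogeneous, with "some patients exhibiting a rapid deterioration and others a slow progressive loss of muscle function". With up to 3 *MTM1* subjects per cohort, one subject's change between the parts can move a group mean.

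The shift tables are the sharper problem. A category that changed before MAD started, and stayed changed, appears as a shift in the MAD period.

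**Working it through.** **Gap between baseline and first MAD dose.** Follow-up is 4 weeks and washout at least 12 weeks (Protocol 3.1.1): 4 + 12 = 16 weeks. This agrees with the visit plan. SAD Week 17 is Day 113, and (113 − 1)/7 = 16.0 weeks; Protocol Table 3 labels that sample "16 weeks post-dose". The ±3-day window gives (110 − 1)/7 = 15.6 to (116 − 1)/7 = 16.4 weeks, so 16 is the nominal minimum. There is no maximum.

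**Share of the interval that precedes MAD.** With gap g and m weeks of MAD treatment, the share is g/(g + m).

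- Week 13 (m = 12), g = 16: 16/28 = 57%.
- Week 25 (m = 24), g = 16: 16/40 = 40%.
- Subjects under the more-than-3-months rule, taking 3 months as 13 weeks and Week 17 as the last SAD visit: g exceeds 16 + 13 = 29, so the shares exceed 29/41 = 71% and 29/53 = 55%.

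These are shares of calendar time, not estimates of bias.

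**Shift tables.** Three possible patterns for one parameter:

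| Pre-SAD | MAD Day 1, pre-dose | Worst in MAD | Shift under SAP 6.2.3 | Shift from MAD baseline |
|---|---|---|---|---|
| Normal | Normal | High | Normal to High | Normal to High |
| Normal | High | High | Normal to High | none |
| High | Normal | High | none | Normal to High |

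The second row counts a pre-MAD change in the MAD period. The third misses one that arises during MAD.

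**Can the reader recover MAD change from the planned tables?** Let Y0, Y1 and Y13 be the pre-SAD, MAD Day 1 and Week 13 values. Then (Y13 − Y0) − (Y1 − Y0) = Y13 − Y1, so subtracting the two tabulated mean changes gives the mean MAD change, but only if both means come from the same subjects. The SD cannot be recovered, because it needs the covariance of the two changes, which is not tabulated. The median, range and shift categories cannot be recovered either.

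**Residual drug at a MAD baseline.** Protocol 1.3.1 gives 2 to 4 weeks for the class and 21 days in monkeys. The terminal-phase residual of the single dose after 112 days is 2^(−112/t½): 0.4% at 14 days, 2.5% at 21 days and 6.25% at 28 days.

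**What is not affected.** AEs are reported separately for SAD and for MAD plus extension (SAP 6.14.1). PK, ADA and GAS use no change from baseline. CGI-I and PGI-C ask about change from the condition before treatment.

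**The case against.** A single drug-naive baseline is a normal reference for cumulative safety in a first-in-human trial where subjects pass from SAD to MAD. It fits Protocol 9.8, so SAP 10 had no clear departure to record. That stands: the choice is legitimate, and a reader who infers an error or a protocol deviation goes further than the documents allow. What is missing is a second reference.

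Protocol 3.2.1 reports from the natural history study that patients are very stable on the trial's assessment measures, dysphagia excepted. That also stands, and it limits how much drift to expect in FVC, MIP and MFM32. It does not speak to effects of the SAD dose itself.

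Observed values are tabulated by visit, individual profiles are plotted and all data are listed, so the MAD Day 1 values are visible. This helps with means, but it does not repair the shift tables or the spread of the changes.

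A reader might infer that leftover SAD drug is being counted as MAD effect. The residuals above are small fractions of the single dose. The main issue is elapsed time, together with any change that began after the single dose and lasted.

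The exploratory Bayesian model in SAP 6.13.10 does address natural course. It does not cover the safety tables, and SAP 10 does not include it in the final reporting.

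**Conclusion.** The point holds in a limited form. For SAD participants, MAD and MAD-extension change tables (laboratory, coagulation, complement, vital signs, ECG, FVC, MIP, Total MFM32), and the shift tables planned for some of these, include at least 16 nominal weeks before the first MAD dose. They cannot isolate the multiple-dose change that the secondary endpoint names. The size of any bias is unknown, because the documents give no drift rate.

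Because MAD3 waits for 12-week data from MAD1 and MAD2, a reader might also infer that the pre-MAD interval lengthens with dose and so confounds the dose comparison. That needs subjects to keep their cohort and MAD3 to have opened. The protocol lets the dose change between parts. SAP 7 says the trial ended before the interim analysis, which Protocol 9.2 ties to Cohorts 1 and 2 completing 12 weeks of MAD, or to a sponsor request. The documents do not show that MAD3 opened.

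Replacement subjects who enter at MAD are a smaller gap. The first sentence of SAP 6.2.3 gives them a pre-MAD baseline, but the second ties baseline to a SAD dose they never receive.

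The change is worth making: it alters reported shifts and summaries and needs no new data.

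**What to change.** In SAP 6.2.3:

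- Keep the pre-SAD baseline as the drug-naive reference for SAD visits and for cumulative change.
- Add a MAD baseline: the last non-missing value before the first MAD dose. Select it by time, since the MAD schedule also takes laboratory samples after the Day 1 infusion.
- Present MAD and MAD-extension change against both baselines, side by side, and do the same for the shift tables where these are planned. Label MAD Week 1 Day 1 pre-dose as the baseline in the MAD columns.
- Reword the second sentence so that replacement subjects entering at MAD use their last value before their own first MAD dose.
- Keep the pre-SAD biopsy as the biopsy baseline for SAD participants, because the schedule gives them no biopsy just before MAD.

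The cost is SAP wording, one baseline flag and a second set of columns. The MAD baseline is not drug-naive, with the residual of about 0.4% to 6% shown above. This is why the pre-SAD columns should stay.
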